**Microbiome-Cytokine Analysis:**

To identify key microbes associated with inflammation in colon cancer we will conduct serum cytokine profiling using the Luminex array platform. Plasma samples will be taken from patients prior to surgery and stored at -80° C. Plasma cytokine concentrations (32 cytokines) will be measured in the laboratory of [name] and [name], who has expertise in conducting cytokine assays and analysis. We will use the Luminex Plate Array. All samples and standards will be run in duplicate and averaged, and calibration curves will be run on each plate using the standards provided. Prior to analysis, we will conduct normality testing for each variable using Shapiro-Wilk test. For any variables that do not pass, a logarithm transformation will be performed. Analysis of circulating cytokine levels will be analyzed using the Kruskall-Wallis test across CSTs by time point, as well as, by linear mixed models to account for the repeated measurements and missing observations using quartiles or dichotomous values of cytokine levels. We will also perform correlation analysis using Spearman correlation on measures of alpha diversity and cytokine levels at baseline, and PERMANOVA for measurement of beta-diversity stratified by level of cytokine

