### **Sample Population:**

Inclusion/exclusion criteria – the study population will be derived from the two participating BSW hospital systems (Waco and Temple, TX) and will be selected to participate in the study on the basis of the following criteria (inclusion): Age  $>18$  and  $\leq 79$  years, written informed consent, ability to perform informed consent, FOLFOX treatment and Stage II/III colon cancer diagnosis. To ensure fitness for recurrence detection and anti-cancer therapy, the age was restricted to  $>18$  so as not to include minors, and  $\leq 79$  years based on life expectancy with colon cancer diagnosis. Individuals will be excluded from participating if any of the following criteria are met: not diagnosed with stage II or III colon cancer, pregnancy, Lynch syndrome or FAP diagnosis, inability or refusal to perform informed consent, inability to comply with the follow-up program, history of previous colon cancer diagnosis, previous treatment with antibiotics in the last month, previous bowel resection.

Sample size - Based on current data from BSW, the recurrence rate for stage II/III colon cancer is 20%, with a 10% 5-year survival rate for stage IV colon cancer. Given our study design, we conducted power calculations for each group. To meet the number required to detect chemotherapy induced diarrhea and mucositis associated with microbial and metabolite abundance, we need to collect at least 560 stool samples from 112 people (Observational Study). To meet the power requirements for detection of differentially abundant microbes and metabolites associated with chemotherapy-induced CID we estimate needing at least 100 stage II/III patients. The specific power calculation for these groups are provided below.

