and microbial clusters (community state types) at baseline using Kruskall-Wallis, and for individual taxa using Pairwise Spearman correlations. We will use PERMANOVA for comparing beta-diversity (weighted UniFrac distances) at baseline by levels of macro- and micronutrients. DESeq2, Kruskall-Wallis and Mann-Whitney tests will be conducted to identify significant differences in tissue and stool taxa or microbial clusters according HEI scores at baseline. The Benjamini and Hochberg false discovery rate (FDR) will be used to correct for multiple testing. Taxa or microbial clusters found to be significantly differentially abundant between treatment time points and baseline will be used to conduct 'random forest' modeling, as previously described, to identify dietary factors that best predict changes in these taxa or clusters. Additionally, we will investigate the tissue and stool microbiome-diet relationship using principal components analysis to identify significant trends among the dietary factors using coinertia analysis. To investigate the microbiome-diet relations during treatment, we will use the microbial clusters and calculate the  $\log_2$  fold change in the clusters from baseline. We will then determine how much the clusters change from baseline according to dichotomous values of macronutrients.

**Microbiome-treatment analysis:** To evaluate differential abundance comparing treatment time points to baseline (prior to surgery and post-surgery/pre-treatment), DESeq2 will be used to control operational taxonomic unit (OTU) over-dispersion between replicates; OTUs will be considered significantly differentially abundant between time points if the false discovery rate (FDR) corrected p-value is below 0.1. A change in relative abundance will be defined as a fold change between mean log relative abundance during treatment phase (week 4, 14, 24) and baseline (prior to surgery). Taxa found to be significantly differentially abundant between treatment time points and baseline (FDR corrected p-value  $<0.05$ ) will be put into an adjusted regression model to control for age, education, income level, marital status, and activity level, diet quality (HEI), tumor stage, medical history with p-values corrected for multiple hypothesis testing using FDR adjustment.

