**Community state type modeling of treatment effect:** As described earlier, in order to reduce data dimensionality and improve power (due to small sample size), we will perform cluster modeling using Dirichlet multinomial mixtures, as well as, use the partitioning around the medoid (pam in R) algorithm. To calculate the dissimilarity matrix for this analysis, we will first calculate weighted UniFrac distance, then this matrix will be dimensionally reduced by choosing the most significant eigenvectors from PCoA analysis. Community state types (CST), which are defined as 'clusters of community samples with similar compositions of microbial taxa', will be obtained from this analysis. Statistical difference in CST abundance between treatment and baseline will be conducted using median values. Plots of CSTs for each subject over time will be used to identify associations between CSTs and incidence of CID, mucositis and severity of side effects. In order to model the dynamics of the CST transitions, we will use Markov chain to estimate the transition probabilities, as demonstrated for vaginal CST associated with pre-term birth. Transition rates between CSTs for each set of paired samples will be calculated using maximum-likelihood estimates. Additionally, differential relative abundance analysis of CSTs between baseline (pre-surgery and pre-treatment) and treatment time points will be conducted using linear mixed models to account for the repeated measurements at the 4 time points and missing observations. To evaluate differences in beta diversity between treatment and baseline the PERMANOVA test will be used. The inferred function of the microbiota will be obtained using the bioinformatics tool PICRUSt, which uses 16S rRNA marker genes to predict presence of gene families and construct a composite metagenome. This method has been used successfully in several similar studies to predict key metabolic functions associated with taxa important in distinguishing disease from healthy controls.

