## 5. Human Subjects

### Protection of Human Subjects

#### A. Human Subjects Involvement and Characteristics

Human subjects involvement: Individuals with a positive diagnosis upon histological examination for colon cancer will be recruited from the Baylor Scott and White McClinton Cancer Center in Waco, TX and The BSWH Temple, TX locations. The Baylor Scott & White McClinton Cancer Center (BSWMCC), in Waco, Texas, and BSWH Clinic in Temple, TX provides ambulatory medical, radiation, and supportive hematology/oncology services to adults five days per week. In addition, the BSWMCC/BSWH Temple Clinics provides on-site laboratory and pharmacy services in conjunction with medical oncology and hematology care and has infusion services. The CRC Group at BSWMCC and BSWH Temple is responsible for the orchestration of day-to-day aspects of clinical research such as patient eligibility, appointments, informed consent, data collection and transcription of information from medical records onto special data collection forms.

- Patients enrolled in this study represent a vulnerable population of terminally or critically ill individuals. For this reason, those staff, Physicians and REAs, will explain with care and clarity that as a patient they will not experience any personal medical benefit from their participation in this study, but that findings may benefit future patients undergoing similar treatment. It will also be made clear that this is an observational study and will in no way impact their treatment or standard of care, and if they choose not to participate will also not affect their treatment in any way.
- Characteristics of subject population: We will recruit 112 stage II/III patients who fit our inclusion criteria (see inclusion/exclusion criteria). Baseline characteristics of current patients undergoing treatment at BSWMCC reflect the demographics of the greater Temple and Waco area: 44.7% White, 30.4% Hispanic and 21.5% Black, 1.7% Asian. During 2016, 109 total CRC cancer cases were treated (Table 1).
- 

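### The repeated-measures cytokine models use quartiles or two groups where continuous values would keep more power, at almost no cost

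*Protocol*

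**What the plan says.** Protocol section 4.4, Microbiome-Cytokine Analysis, describes a Luminex assay: "Plasma cytokine concentrations (32 cytokines) will be measured". Each variable is tested for normality with Shapiro-Wilk, and "For any variables that do not pass, a logarithm transformation will be performed".

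Three kinds of analysis follow:

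- A rank test at each visit: "Analysis of circulating cytokine levels will be analyzed using the Kruskall-Wallis test across CSTs by time point".
- Linear mixed models, meant to deal with repeated measurements and missing values, "using quartiles or dichotomous values of cytokine levels".
- At baseline, Spearman correlation of cytokines with alpha diversity. A PERMANOVA of beta diversity by cytokine level is also planned.

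The paragraph does not say which grouping applies, where a two-group cut falls, or whether the cytokine is the outcome or a predictor in the mixed model.

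The Microbiome-Diet Analysis in the same section does something similar for the treatment period. It will determine "how much the clusters change from baseline according to dichotomous values of macronutrients".

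Elsewhere in section 4.4, under Community state type modeling of treatment effect, clustering is justified by the wish to "reduce data dimensionality and improve power (due to small sample size"). Planned enrolment is 112 ("We will recruit 112 stage II/III patients who fit our inclusion criteria", section 5), and section 4 gives a minimum of 100 ("we estimate needing at least 100 stage II/III patients").

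**The concern.** Cutting a continuous measurement into groups treats all patients within a group as alike and so discards information. Two features of the protocol make the choice hard to defend here. First, the log transform already provides a scale for a continuous analysis. Grouping makes that step idle in the mixed model, because quantile groups are the same before and after a log transform. Second, the protocol elsewhere gives small sample size as a reason to seek power, and grouping works against that.

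What is at stake is Sub-Aim 1c, which concerns cytokine levels before and during treatment. The mixed model is the only cytokine analysis stated to use the repeated visits together and to allow for missing values. The rank test takes each visit separately, and the Spearman correlation covers baseline only.

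**Working it through.** The protocol gives no power, effect size or variance for cytokines, and its power table concerns taxa abundance. There is therefore no stated figure to reproduce.

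**Assumptions, all mine:** the cytokine is normal on the analysis scale; its relation to the other variable is linear; each patient contributes one independent value; two-sided alpha is 0.05; and the association is one that a continuous analysis detects with 80% power. From the protocol: N = 112, with 100 as the minimum.

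**1. Information kept after grouping.** For a standard normal variable this is the sum over groups of p × m², where p is the share of patients in the group and m the group mean.

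- Median split: the group means are ±√(2/π) = ±0.798, so 2/π = 0.637 is kept and 36.3% is lost.
- Two groups cut at a quartile: 0.25 × 1.271² + 0.75 × 0.424² = 0.539 kept, 46.1% lost.
- Four quartile groups: 0.25 × 2 × (1.271² + 0.325²) = 0.861 kept, 13.9% lost.
- Quartiles scored 1 to 4: squared correlation with the original variable = 1.0345² / 1.25 = 0.856, so 14.4% lost.

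Other two-group cuts lose more than the median split: 37.8% at 40/60, 40.5% at a tertile, 51.0% at 20/80 and 65.8% at 10/90. Under normality, 36% is therefore the smallest loss from a two-group cut.

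**2. Effective number of patients.** 112 × 0.637 = about 71 for a median split; 112 × 0.861 = about 96 for quartiles.

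**3. Power.** With Fisher's z, power = Φ(atanh(r) × √(N − 3) − 1.96). For N = 112, 80% power corresponds to r = 0.262. A grouped variable has r multiplied by the square root of the information kept.

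| Form of the cytokine | Attenuated r | Power |
|---|---|---|
| Continuous | 0.262 | 80% |
| Quartiles scored 1 to 4 | 0.262 × √0.856 = 0.242 | 73% |
| Median split | 0.262 × √0.637 = 0.209 | 60% |
| Two groups cut at a quartile | 0.262 × √0.539 = 0.192 | 53% |

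Quartiles entered as three indicators need a 3-degree-of-freedom test. Here R² = 0.262² × 0.861 = 0.059, the noncentrality is 112 × 0.059 / (1 − 0.059) = 7.0, and the noncentral F with 3 and 108 degrees of freedom gives 57.5%. That is slightly below the median split, because the extra degrees of freedom cost more than the finer grouping saves.

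With N = 100, r becomes 0.277 and the powers agree to within 0.2 percentage points.

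**4. Sensitivity to shape.** If the relation is linear on the raw scale and the variable is not normal, a median split loses 25% (uniform), 50% (Laplace), 52% (exponential) or 73% (lognormal with log-SD 1).

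**The case against.** Several points on the other side stand.

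- Cytokines are a secondary outcome in a study that section 3 calls formative. The Kruskal-Wallis and baseline Spearman analyses keep them ungrouped, so not every cytokine result is affected.
- The figures are illustrative. The model is a repeated-measures model with up to five blood draws (section 4.1, item B), and the effective numbers above assume one value per patient.
- Grouping can be reasonable for an analyte that is mostly below its detection limit.
- The choice of cut could be fixed in a statistical analysis plan. The lack of a cut point is therefore not the complaint, and a reader who infers that the cut will be picked after seeing results across 32 cytokines goes beyond what the protocol shows. The point is that the protocol itself commits to grouping, and both alternatives it names lose information.

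Three other stronger readings are tempting. One is that a linear mixed model is mis-specified for a 0/1 value; this holds only if the cytokine is the outcome, which the protocol does not say. Another is that Aim 2 is harmed by dichotomised macronutrients. Aim 2 asks about diet and chemotherapy-induced diarrhoea, whereas the sentence in question relates macronutrients to change in microbial clusters. The diet section also plans Spearman, random forest and coinertia analyses that are not said to dichotomise nutrients. The third is that cytokines are always log-transformed first; the transform applies only to variables that fail Shapiro-Wilk.

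**Conclusion.** The point holds as a modest, nearly free improvement to one secondary analysis. The protocol fixes a grouped form for the only cytokine analysis stated to handle repeated measures and missing data, where a continuous form is available. Under the stated assumptions the loss is about 14% of the information with quartiles and at least 36% with two groups. Nominal power of 80% falls to 73% or 57.5% with quartiles, depending on coding, and to 60% or less with two groups. A reader might take 36% as a ceiling; it is the floor for two-group cuts of a normal variable, and other shapes move it in both directions. The direction of the effect is secure as long as the relation is roughly linear on the analysis scale. The exact size in the repeated-measures model cannot be derived from the protocol.

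**What to change.** In section 4.4, Microbiome-Cytokine Analysis, enter cytokines in the mixed models as continuous values, log-transformed where needed, with a spline if the relation is non-linear. State whether the cytokine is the outcome or a predictor. Keep categories for display, or for analytes mostly below the detection limit. If a dichotomised cytokine is ever the outcome, use a logistic mixed model.

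In the Microbiome-Diet Analysis, relate the log2 fold change of the clusters to continuous macronutrient intake.

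The cost is a change of wording and a check of linearity. No further patients, samples or visits are needed.

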## 5. Human Subjects

### Protection of Human Subjects

#### A. Human Subjects Involvement and Characteristics

Human subjects involvement: Individuals with a positive diagnosis upon histological examination for colon cancer will be recruited from the Baylor Scott and White McClinton Cancer Center in Waco, TX and The BSWH Temple, TX locations. The Baylor Scott & White McClinton Cancer Center (BSWMCC), in Waco, Texas, and BSWH Clinic in Temple, TX provides ambulatory medical, radiation, and supportive hematology/oncology services to adults five days per week. In addition, the BSWMCC/BSWH Temple Clinics provides on-site laboratory and pharmacy services in conjunction with medical oncology and hematology care and has infusion services. The CRC Group at BSWMCC and BSWH Temple is responsible for the orchestration of day-to-day aspects of clinical research such as patient eligibility, appointments, informed consent, data collection and transcription of information from medical records onto special data collection forms.

- Patients enrolled in this study represent a vulnerable population of terminally or critically ill individuals. For this reason, those staff, Physicians and REAs, will explain with care and clarity that as a patient they will not experience any personal medical benefit from their participation in this study, but that findings may benefit future patients undergoing similar treatment. It will also be made clear that this is an observational study and will in no way impact their treatment or standard of care, and if they choose not to participate will also not affect their treatment in any way.
- Characteristics of subject population: We will recruit 112 stage II/III patients who fit our inclusion criteria (see inclusion/exclusion criteria). Baseline characteristics of current patients undergoing treatment at BSWMCC reflect the demographics of the greater Temple and Waco area: 44.7% White, 30.4% Hispanic and 21.5% Black, 1.7% Asian. During 2016, 109 total CRC cancer cases were treated (Table 1).
- 

**Table 1. 2016 Colorectal Adenocarcinomas (BSWH)\***

Characteristic	N (%)
Stage	
I	3(3)
II	25(23)

III	56(51)
IV	25(23)
Sex	
M	43(39)
F	66(61)
Race/Ethnicity	
Non-Hispanic white	74(68)
African-American	21(19)
Hispanic	11(10)
American Indian	3(3)

\*Combined Temple and Waco locations

#### B. Potential Risks

- Potential risk: potential risks associated with this study are no higher than the risk of completing these procedures for the anti-cancer treatment they will undergoing. The alternatives to this procedure introduces greater risk and requires discomfort of a rectal exam and additional clinical visit. Subjects may choose to not participate in the voluntary study.
- Potential benefits: patients may benefit from this study by learning about their dietary history and regular dietary habits, and the potential effects on their response to therapy and type of and severity of side-effects. They may be able to use this information to reduce side-effects that may be a result of diet-treatment interactions.

